## 4.3 Event Monitoring/Survival Follow-up

	Event Monitoring Phase 				
	q. 3 months until PD	At PD	After PD q. 6 months	Death	New Primary
Event Monitoring	X	X	X	X	At each occurrence

1. If a patient is still alive 5 years after registration, no further follow-up is required.

## 5.0 Grouping Factor

5.1 BRAF status: Mutant (Arm A) versus wildtype (Arm B) vs. mutant or wildtype (Arm C)

## 6.0 Registration/Randomization Procedures

## 6.1 Pre-Registration

## 6.11 Pre-registering a patient

**Non Mayo Clinic sites only:**

To register a patient, fax [REDACTED] a completed eligibility checklist to the Mayo Clinic Research Site Management Office between 8 a.m. and 5 p.m. Central Time Monday through Friday.

**Mayo Clinic sites only:**

To register a patient, access the Mayo Clinic Research Registration application. The registration application is available 24 hours a day, 7 days a week. Back up and/or system support contact information is available on the website. If unable to access the website, call the MCR Research Site Management Office at [REDACTED] [REDACTED] between the hours of 8 a.m. and 5:00 p.m. Central Time (Monday through Friday).

Access and training instructions for the Research Registration Application are available on the Office of Clinical Trials web page

[REDACTED] and detail the process for completing and confirming patient registration. Prior to initiation of protocol treatment, this process must be completed in its entirety and an MCCC subject ID number must be available as noted in the instructions. It is the responsibility of the individual and institution registering the patient to confirm the process has been successfully completed prior to release of the study agent. Patient registration via the Research Registration Application can be confirmed in any of the following ways:

- Contact the Research Site Management Office [REDACTED]. If the patient was fully registered, the MCCC Research Site Management Office staff can access the information from the centralized database and confirm the registration.
- Refer to “Instructions for Remote Registration” in section “Finding/Displaying Information about A Registered Subject.”

**All institutions**

## 6.12 Correlative studies (All institutions)

A mandatory correlative research component is part of this study. The patient will be automatically registered onto this component (see Sections 3.1 and 17.0).

## 6.13 Verification (All institutions)

Prior to accepting the pre-registration, the registration/randomization application will verify the following:

- IRB approval at the registering institution
- Patient pre-registration eligibility
- Existence of a signed consent form
- Existence of a signed authorization for use and disclosure of protected health information.

## 6.14 Pre-registration tests/procedures (All institutions)

Pre-registration tests/procedures (see Section 4.0) must be completed within the guidelines specified on the test schedule.

## 6.2 Registration Requirements

## 6.21 Registering a patient

**Non Mayo Clinic sites only:**

To register a patient, fax [REDACTED] a completed eligibility checklist to the Mayo Clinic Research Site Management Office between 8 a.m. and 5 p.m. Central Time Monday through Friday.

**Mayo Clinic sites only:**

To register a patient, access the Mayo Clinic Research Registration Application at [REDACTED]. The Research Registration Application is available 24 hours a day, 7 days a week. Back up and/or system support contact information is available on the website. If unable to access the website, call the Research Site Management Office at [REDACTED] between the hours of 8 a.m. and 5 p.m. Central Time (Monday through Friday).

The instructions for the Research Registration Application are available on the Office of Clinical Trials web page [REDACTED]

[REDACTED] and confirming patient registration. Prior to initiation of protocol treatment, this process must be completed in its entirety and an MCCC subject ID number must be available as noted in the instructions. It is the responsibility of the individual registering the patient to confirm the process has been successfully completed prior to release of the study agent. Patient registration via the Research Registration Application can be confirmed in any of the following ways:

- Contact the Research Site Management Office [REDACTED]. If the patient was fully registered, the Research Site Management Office staff can access the information from the centralized database and confirm the registration.
- Refer to “Instructions for Remote Registration” in section “Finding/Displaying Information about A Registered Subject.”

- 6.22 Correlative studies (All institutions)
- 6.221 A mandatory correlative research component is part of this study. The patient will be automatically registered onto this component (see Sections 3.1, 14.0 and 17.0).
- 6.222 An optional correlative research component is part of this study. There will be an option to select if the patient is to be registered onto this component (see Section 17.0)
- Patient has/has not given permission to give his/her tissue sample for research testing.
- 6.223 At the time of registration, the following will be recorded:
- Patient has/has not given permission to store and use his/her sample(s) for future research at Mayo Clinic.
  - Patient has/has not given permission to store and use his/her sample(s) for future research to learn, prevent, or treat other health problems.
  - Patient has/has not given permission for MCCC to give his/her sample(s) to researchers at other institutions.

#### **All institutions**

- 6.23 IRB approvals
- Documentation of IRB approval must be on file in the Research Site Management Office before an investigator may register any patients.
- In addition to submitting initial IRB approval documents, ongoing IRB approval documentation must be on file (no less than annually) at the Research Site Management Office [REDACTED]. If the necessary documentation is not submitted in advance of attempting patient registration, the registration will not be accepted and the patient may not be enrolled in the protocol until the situation is resolved.
- When the study has been permanently closed to patient enrollment, submission of annual IRB approvals to the Research Site Management Office is no longer necessary.
- 6.24 Verification
- At the time of registration, the Research Registration Application will verify the following:
- IRB approval
  - Patient eligibility
- 6.25 Pretreatment tests/procedures (see Section 4.0) must be completed within the guidelines specified on the test schedule.
- 6.26 Consent and treatment on this protocol must commence at Mayo Clinic Rochester or a participating site under the supervision of a medical oncologist.
- 6.27 Treatment cannot begin prior to registration and must begin  $\leq 14$  days after registration.
- 6.28 All required baseline symptoms (see Section 10.6) must be documented and graded.
- 6.29 Blood draw/biospecimen kits must be available on site for patients being treated outside of Mayo Clinic in Rochester, MN.

### 6.3 Trial Rules

The clinical trial will be conducted in compliance with regulations (21 CFR 312, 50, and 56), guidelines for Good Clinical Practice (ICH Guidance E6), and in accordance with general ethical principles outlined in the Declaration of Helsinki; informed consent will be obtained from all participating patients; the protocol and any amendments will be subject to approval by the designated IRB prior to implementation, in accordance with 21 CFR 56.103(a); and subject records will be stored in a secure location and subject confidentiality will be maintained. The investigator will be thoroughly familiar with the appropriate use of the study drug as described in the protocol and Investigator's Brochure. Essential clinical documents will be maintained to demonstrate the validity of the study and the integrity of the data collected. Master files should be established at the beginning of the study, maintained for the duration of the study and retained according to the appropriate regulations.

## 7.0 Protocol Treatment

### 7.1 Neoadjuvant Treatment Schedule

#### 7.11 Arm A: BRAF mutant disease

##### Cycle 1 only

Agent	Dose	Route	Day
Vemurafenib (VEM)	960 mg	PO BID	Days 1-22
	720 mg	PO BID	Days 23-28
Cobimetinib (COBI)	60 mg	PO QD	Days 1-21

##### Cycle 2 and beyond for a maximum of 2 cycles

Agent	Dose	Route	Days
Vemurafenib (VEM)	720 mg	PO BID	Days 1-28
Cobimetinib (COBI)	60 mg	PO QD	Days 1-21
Atezolizumab (ATEZO)	840 mg	IV	Days 1, 15 ( $\pm 3$ days)

Cycle = 28  $\pm 3$  days; PO = by mouth; BID= twice daily; QD = once daily; IV= intravenous

#### 7.111 General instructions for oral agents

Oral agents (vemurafenib and cobimetinib) may be taken at the same time for the morning dose.

Both agents may be taken with or without food

Do not chew or crush tablets

#### 7.112 Missed dose instructions for oral agents

If patient misses a dose or vomits the dose, do not make up the dose. Resume treatment with next scheduled dose.

#### 7.12 Arm B: BRAF wild-type disease (maximum of 3 cycles)

Agent	Dose	Route	Day
Cobimetinib (COBI)	60 mg	PO QD	Days 1-21 ( $\pm 3$ days)
Atezolizumab (ATEZO)	840 mg	IV	Days 1, 15 ( $\pm 3$ days)

Cycle = 28  $\pm 3$  days; PO = by mouth; QD = once daily; IV= intravenous

#### 7.13 Arm C: BRAF wild-type or BRAF mutant disease (maximum of 4 cycles)

No premedication is indicated for the administration of Cycle 1 of atezolizumab or tiragolumab. Premedication with antihistamines, antipyretics, and/or analgesics may be administered for the second and subsequent atezolizumab infusions only, at the discretion of the investigator.

Agent	Dose	Route	Day
Atezolizumab (ATEZO)	1200 mg	IV	Day 1 ( $\pm 3$ days)
Tiragolumab (TIRA)	600 mg	IV	Day 1 ( $\pm 3$ days)

Cycle = 21  $\pm 3$  days; IV= intravenous

Atezolizumab should be infused over 30 ( $\pm 10$ ) minutes if the previous infusion was tolerated without an infusion related reaction (IRR) or 60 ( $\pm 15$ ) minutes if the patient experienced an IRR with the previous infusion. The infusion will be followed by a 60-minute observation period.

If the patient tolerated the previous atezolizumab infusion well, without infusion-associated adverse events, the observation period after the next and following infusions may be reduced to 30 minutes.

If the patient experienced infusion-associated adverse events in the previous infusion, the observation period should be 60 minutes.

Following the administration of atezolizumab and a 60-minute or 30 minute observation period, patients will receive 600 mg tiragolumab administered by IV infusion over 60 ( $\pm 15$ ) minutes on Day 1 of each 21-day cycle. The infusion will be followed by a 60-minute observation period.

Tiragolumab should be infused over 30 ( $\pm 10$ ) minutes if the previous infusion was tolerated without an infusion-related reaction, or 60 ( $\pm 15$ ) minutes if the patient experienced an infusion-related reaction with the previous infusion.

In addition, if the first infusion of tiragolumab was well-tolerated (with no infusion-related reaction), the observation period for subsequent tiragolumab infusions may be reduced to 30 minutes.

## 7.2 Surgery

Within 2-4 weeks of completing neoadjuvant therapy, patients with resectable disease should undergo surgery. Operation will include all affected regional nodal basins based on clinical and radiologic evaluation. Surgeons will identify the clipped node separately from the remainder of the surgical specimen to permit separate histologic assessment of the index clipped node. Guidelines for the performance of therapeutic lymph node dissection based on site of disease are as follows:

### 7.21 Axillary dissection

A complete axillary lymph node dissection to include all levels of the axilla is recommended. The dissection should be governed by anatomic boundaries. Lymph node bearing tissue should be resected from within the following margins. The superior margin of dissection includes the axillary vein from the thoracic inlet (Halsted's ligament) to the latissimus dorsi tendon. The medial margin is the intercostal and serratus anterior muscles on the chest wall. The lateral margin is the edge of the latissimus dorsi muscle including those nodes which lie lateral to the thoracodorsal neurovascular bundle proximally. The inferior border is approximately the fourth intercostal space. The deep margin should be the subscapularis muscle. The long thoracic, medial pectoral and thoracodorsal nerves should be preserved.

### 7.22 Inguinal dissection

An inguinal lymph node dissection should be performed according to standard technique with respect to the following anatomic boundaries. All of the lymph node bearing tissue should be resected from within the following margins. The superior margin should be at least 5 cm proximal to the inguinal ligament. The inferior margin is the adductor hiatus (Hunter's canal). The medial margin should expose the edge of the adductor magnus muscle and the lateral margin is the

sartorius muscle. The femoral nerve and vessels should be preserved whenever possible.

- 7.23 Pelvic (iliac (external and internal [hypogastric]) and obturator) dissection  
A deep inguinal or pelvic lymph node dissection of the iliac (both external and internal or hypogastric) and obturator nodes should be performed when there is evidence of disease by imaging or may be performed electively for bulky disease but is not required if anatomic and functional imaging are negative. A standard anatomic approach is recommended. When disease is identified by preoperative imaging, every effort should be made to extirpate these affected nodes in addition to all the fatty alveolar lymph node containing tissue from the femoral canal distally to the level of the common iliac bifurcation proximally. The femoral and obturator nerves should be spared.
- 7.24 Popliteal dissection  
A therapeutic popliteal lymph node dissection consists of removal of the lymph node bearing tissue from the popliteal fossa within the following anatomic boundaries. The superior margin of dissection includes the biceps femoris and semimembranosus and semitendinosus muscles. The medial margin is made up of the semimembranosus and semitendinosus muscles. The lateral margin is the biceps femoris muscle. The inferior margins are delineated by the lateral and medial heads of the gastrocnemius muscles.
- 7.25 Cervical dissection  
A modified radical neck dissection preserving the spinal accessory nerve and sternocleidomastoid muscle is recommended. A superficial parotidectomy should be performed for peri- or intraparotid nodal disease and considered for patients with primary tumors of the face, ear or anterior scalp but might be guided by clinical examination and imaging findings including lymphoscintigraphy if performed. The lymph node bearing tissue from within the following anatomic borders should be resected: inferior to the clavicle, superior to the mandible, mastoid, parotid gland tail, posterior to the anterior border of the trapezius muscle, and anterior to the strap muscles. The contents of the posterior triangle should be resected with preservation of the spinal accessory nerve whenever possible. A posterior or posterolateral neck dissection with extension of the boundaries to include all of the fibrofatty nodal tissue deep to the trapezius fascia cephalad to include suboccipital and possibly retroarticular nodes and deep to include the splenius capitis, levator scapulae, and semispinalis capitis muscles may be appropriate for posterior cervical disease.
- 7.26 Management of disease in interval nodes  
Patients with disease identified in interval or ectopic sites such as the triangular intermuscular space, the fatty and alveolar tissue around the affected node or nodes should be widely excised and consideration given to dissection of the closest proximal draining basin.

7.3 Adjuvant Treatment: Completely resected patients (All Arms)

Agent	Dose	Route	Day	ReRx
Atezolizumab (ATEZO)	1200 mg	IV	Day 1 ( $\pm 3$ days)	Q3w for a maximum of 8 cycles

Cycle = 21  $\pm 3$  days; IV= intravenous

## 8.0 Dosage Modification Based on Adverse Events

Strictly follow the modifications in this table during neoadjuvant therapy. For adjuvant therapy, these modifications should be regarded as guidelines to produce mild-to-moderate, but not debilitating, side effects. If multiple adverse events are seen, administer dose based on greatest reduction required for any single adverse event observed. Reductions or increases apply to treatment given in the preceding cycle and are based on adverse events observed since the prior dose.

→ **ALERT:** ADR reporting may be required for some adverse events (See Section 10.0) ←

### 8.1 Dose Levels (Based on Adverse Events in Tables 8.2 and 8.3)

Please note there are no dose reductions for atezolizumab or tiragolumab

\*Dose level 0 refers to the starting dose.

#### 8.11 Dose levels for Vemurafenib

Dose Level	Vemurafenib (Cycle 1, D1-21)	Vemurafenib (Cycle 1, D22-28, Cycles 2-3)
0*	960 mg by mouth twice daily	720 mg by mouth twice daily
-1	720 mg by mouth twice daily	480 mg by mouth twice daily
-2	480 mg by mouth twice daily	240 mg by mouth twice daily

#### 8.12 Dose levels for Cobimetinib

Dose level	0*	-1	-2
Cobimetinib	60 mg by mouth once daily	40 mg by mouth once daily	20 mg by mouth once daily

→ → Use the NCI Common Terminology Criteria for Adverse Events (CTCAE) current version 4.0\* unless otherwise specified ← ←

\* Located at [REDACTED]

### 8.13 General guidance for dose modifications and treatment delays and discontinuation

There will be **no** dose modifications for **atezolizumab or tiragolumab**.

The dose of **cobimetinib** can be reduced by 20 mg (one dose level) up to two times (i.e., from 60 mg to 40 mg and then from 40 mg to 20 mg). If further dose reduction is indicated after two dose reductions, the patient must discontinue cobimetinib but may continue treatment with atezolizumab and/or vemurafenib at the investigator's discretion.

For BRAFm cohort (Arm A), the dose of **vemurafenib** can be reduced by 240 mg BID (i.e., 480 mg/day) (one dose level) up to two times (i.e., from 960 mg to 720 mg BID and then from 720 mg to 480 mg BID for Cycle 1 OR from 720 mg to 480 mg to 240 mg BID for subsequent neoadjuvant treatment cycles. If further dose reduction is indicated after two dose reductions, the patient must discontinue vemurafenib but may continue treatment with atezolizumab and/or cobimetinib at the investigator's discretion.

If **atezolizumab or tiragolumab** is withheld and corticosteroids are initiated for treatment of an adverse event, corticosteroids should be tapered over  $\geq 1$  month to  $\leq 10$  mg/day oral prednisone or equivalent before atezolizumab can be resumed. If atezolizumab is withheld for  $>105$  days, the patient should be discontinued from atezolizumab. Study treatment may be withheld for  $>105$  days to allow for patients to taper off corticosteroids prior to resuming treatment. Atezolizumab can be resumed after being withheld for  $>105$  days if the investigator agrees that the patient is likely to derive clinical benefit.

If either **cobimetinib or vemurafenib** is withheld for  $\geq 28$  days because of toxicity, the patient should be discontinued from that drug, unless resumption of treatment is approved by the principal investigator after discussion with the investigator.

For BRAFwt cohort (Arm B), if **atezolizumab** is discontinued during neoadjuvant period, then cobimetinib should be discontinued, as single agent activity is not expected.

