### 8.21 Table for Arms A and B only

CTCAE System/Organ/Class (SOC)	ADVERSE EVENTS/SYMPTOMS	ACTIONS		
		Vemurafenib (BRAF-mutant only)	Cobimetinib	Atezolizumab (All patients)
Cardiac Disorders	Heart failure OR Left ventricular systolic dysfunction Clinically asymptomatic LVEF <40% or 40-49% and >10% decrease from baseline	Continue	Omit x 2 weeks repeat LVEF assessment If LVEF > LLN and absolute LVEF <10% decrease from baseline – resume with dose reduced -1 dose level If LVEF < LLN or $\geq 10\%$ decrease from baseline, discontinue	Continue

CTCAE System/Organ/Class (SOC)	ADVERSE EVENTS/SYMPTOMS	ACTIONS		
		Vemurafenib (BRAF-mutant only)	Cobimetinib	Atezolizumab (All patients)
Cardiac Disorders	Clinically symptomatic	Continue	Omit x 4 weeks repeat LVEF assessment If asymptomatic after 4 weeks and repeat LVEF shows >LLN and <10% decrease from baseline, resume with dose reduced -1 dose level If LVEF <LLN or ≥10% decrease from baseline, discontinue.	Omit until myocarditis is ruled out by Cardiology
Endocrine disorders	Adrenal insufficiency Grade ≥2	Continue	Continue	Omit until improves to ≤Grade 1 Discontinue if not improved within 12 weeks Refer to endocrinologist
Endocrine disorders	Hyperglycemia Grade 3-4	Continue	Continue	Omit and initiate treatment under endocrinologist care Resume when symptoms resolve and glucose levels are stable
Endocrine disorders	Hyperthyroidism Grade ≥2 or TSH < 0.1 mU/L	Continue	Continue	Omit and initiate therapy under endocrinologist care Resume when symptoms resolve to ≤Grade 1 Refer to Endocrinology
Endocrine disorders	Endocrine disorders, other specify Symptomatic Hypophysitis	Continue	Continue	Omit and refer to endocrinologist Resume when symptoms resolve to ≤Grade 1
Eye disorders (refer to Ophthalmology)	Blurred vision or Eye pain or Uveitis or Eye disorders-other specify: iritis (immune-related) Grade 2	Continue	Continue	Omit Resume when symptoms resolve to ≤Grade 1

CTCAE System/Organ/Class (SOC)	ADVERSE EVENTS/SYMPTOMS	ACTIONS		
		Vemurafenib (BRAF-mutant only)	Cobimetinib	Atezolizumab (All patients)
Eye disorders (refer to Ophthalmology)	Grade $\geq 3$	Omit until $\leq$ Grade 1 Resume with dose reduced by 1 level once $\leq$ Grade 1	Omit until $\leq$ Grade 1 Resume at same dose once $\leq$ Grade 1	Discontinue

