#### 8.22 Table for Arm C only: Atezolizumab and Tiragolumab

If either study drug is delayed for a related toxicity, it is recommended that the other study drug is also delayed since the safety profiles for atezolizumab and tiragolumab are similar.

In case of delays in dosing of one study drug for drug-related toxicity while the other study drug is given as planned, it is recommended that the study drug being delayed will be administered at the next scheduled infusion (i.e., at the next scheduled 21-day cycle).

CTCAE System/Organ/Class (SOC)	ADVERSE EVENTS/SYMPTOMS	ACTIONS	
		Tiragolumab	Atezolizumab
Cardiac Disorders	Any which are clinically symptomatic	Omit until myocarditis is ruled out by Cardiology	Omit until myocarditis is ruled out by Cardiology
Endocrine disorders	Adrenal insufficiency Grade $\geq 2$	Omit until improves to $\leq$ Grade 1 Discontinue if not improved within 12 weeks Refer to endocrinologist	Omit until improves to $\leq$ Grade 1 Discontinue if not improved within 12 weeks Refer to endocrinologist
Endocrine disorders	Hyperglycemia Grade 3-4	Omit and initiate treatment under endocrinologist care Resume when symptoms resolve and glucose levels are stable	Omit and initiate treatment under endocrinologist care Resume when symptoms resolve and glucose levels are stable
Endocrine disorders	Hyperthyroidism Grade $\geq 2$ or TSH $< 0.1$ mU/L	Omit and initiate therapy under endocrinologist care Resume when symptoms resolve to $\leq$ Grade 1 Refer to Endocrinology	Omit and initiate therapy under endocrinologist care Resume when symptoms resolve to $\leq$ Grade 1 Refer to Endocrinology

CTCAE System/Organ/Class (SOC)	ADVERSE EVENTS/SYMPTOMS	ACTIONS	
		Tiragolumab	Atezolizumab
Endocrine disorders	Endocrine disorders, other specify Symptomatic Hypophysitis	Omit and refer to endocrinologist Resume when symptoms resolve to $\leq$ Grade 1	Omit and refer to endocrinologist Resume when symptoms resolve to $\leq$ Grade 1
Eye disorders (refer to Ophthalmology)	Blurred vision or Eye pain or Uveitis or Eye disorders-other specify: iritis (immune-related) Grade 2	Omit Resume when symptoms resolve to $\leq$ Grade 1	Omit Resume when symptoms resolve to $\leq$ Grade 1
	Grade $\geq 3$	Omit until $\leq$ Grade 1	Discontinue
Gastrointestinal disorders	Diarrhea/Colitis Grade 2	Omit and resume when symptoms resolve to $\leq$ Grade 1	Omit and resume when symptoms resolve to $\leq$ Grade 1

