	Grade 3 (AST/ALT $>5.0$ - $10.0$ x ULN)	Omit and initiate systemic steroid treatment (see Section 9.0) Consult Hepatology if not improving within 1 week Resume when symptoms resolve to $\leq$ Grade 1	Omit and initiate systemic steroid treatment (see Section 9.0) Consult Hepatology if not improving within 1 week Resume when symptoms resolve to $\leq$ Grade 1
	Grade 3+ (AST/ALT $>10.0$ x ULN)	Discontinue Consult Hepatology	Discontinue Consult Hepatology
Investigations	Blood bilirubin increased Total bilirubin $>2$ x ULN For patients with Gilbert's syndrome: modify dose only if direct bilirubin is $>2$ x ULN	Discontinue Consult Hepatology	Discontinue Consult Hepatology
Investigations	Lymphocyte count decreased Grade 4	Omit until $\leq$ Grade 2 Resume once $\leq$ Grade 2	Omit until $\leq$ Grade 2 Resume once $\leq$ Grade 2
Renal and urinary disorders	Acute kidney injury Grade 2	Omit until $\leq$ Grade 1 Resume when symptoms resolve to $\leq$ Grade 1	Omit until $\leq$ Grade 1 Resume when symptoms resolve to $\leq$ Grade 1

CTCAE System/Organ/Class (SOC)	ADVERSE EVENTS/SYMPTOMS	ACTIONS	
		Tiragolumab	Atezolizumab
Renal and urinary disorders	Grade $\geq 3$	Discontinue	Discontinue
Respiratory, thoracic and mediastinal disorders	Pneumonitis Grade 2	Omit until $\leq$ Grade 1 Resume once symptoms resolve to $\leq$ Grade 1	Omit until $\leq$ Grade 1 Resume once symptoms resolve to $\leq$ Grade 1
	Grade $\geq 3$	Discontinue	Discontinue
Skin and subcutaneous tissue disorders	Erythema multiforme Grade $\geq 3$	Omit and initiate supportive care per Section 9.0 Refer to Dermatology	Omit and initiate supportive care per Section 9.0 Refer to Dermatology
Skin and subcutaneous tissue disorders	Rash acneiform Grade 2	Continue Initiate supportive care per Section 9.0 Refer to Dermatology if does not improve to $\leq$ Grade 1 within 2 weeks	Continue Initiate supportive care per Section 9.0 Refer to Dermatology if does not improve to $\leq$ Grade 1 within 2 weeks
	Grade 3	Omit and initiate supportive care per Section 9.0 Refer to Dermatology Resume once $\leq$ Grade 1	Omit and initiate supportive care per Section 9.0 Refer to Dermatology Resume once $\leq$ Grade 1
	Grade 4	Omit and initiate supportive care per Section 9.0 Refer to Dermatology Resume once $\leq$ Grade 1	Omit and initiate supportive care per Section 9.0 Refer to Dermatology Resume once $\leq$ Grade 1

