9.66 Liver Dysfunction

- 9.661 For patients without hepatocellular carcinoma (HCC) any hepatic event:  
Grade 1: Monitor LFTs until values resolve to within normal limits or to baseline values  
Grade 2:  
All events - Monitor LFTs more frequently until values resolve to baseline values  
Events of >5 days' duration:  
Initiate treatment with corticosteroids equivalent to 1-2 mg/kg/day oral prednisone  
Grade 3 or 4:  
Consider patient referral to gastrointestinal specialist for evaluation and liver biopsy to establish etiology of hepatic injury.  
Initiate treatment with corticosteroids equivalent to 1-2 mg/kg/day oral prednisone.  
If event does not improve within 48 hours after initiating corticosteroids, consider adding an immunosuppressive agent.  
If event resolves to Grade 1 or better, taper corticosteroids over  $\geq 1$  month.
- 9.662 For patients with hepatocellular carcinoma (HCC):
  - 9.6621 If any of the following are true:
    - AST/ALT is within normal limits at baseline and increases to  $> 3 \times \text{ULN}$  to  $\leq 10 \times \text{ULN}$
    - or**

AST/ALT is  $> \text{ULN}$  to  $\leq 3 \times \text{ULN}$  at baseline and increases to  $> 5 \times \text{ULN}$  to  $\leq 10 \times \text{ULN}$

**or**

AST/ALT is  $> 3 \times \text{ULN}$  to  $\leq 5 \times \text{ULN}$  at baseline and increases to  $> 8 \times \text{ULN}$  to  $\leq 10 \times \text{ULN}$

Then:

Monitor LFTs more frequently until resolution to baseline values

For events of  $> 5$  days' duration:

Consider initiating systemic steroid therapy at 1-2 mg/kg/day of prednisone or equivalent.

9.6622 AST or ALT  $> 10 \times \text{ULN}$  or bilirubin  $> 3 \times \text{ULN}$ :

Initiate treatment with equivalent to 1-2 mg/kg/day oral prednisone.

If no improvement within 48 hours consider addition of immunosuppressive agent.

If event resolves to baseline, taper corticosteroids over  $\geq 1$  month.

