**10.561 Adverse Events of Special Interest specific to Atezolizumab and/or Tiragolumab:**

- Pneumonitis
- Colitis
- Endocrinopathies: diabetes mellitus, pancreatitis, adrenal insufficiency, hyperthyroidism, and hypophysitis
- Hepatitis, including AST or ALT > 10 × ULN
- Systemic lupus erythematosus
- Neurological disorders: Guillain-Barré syndrome, myasthenic syndrome or myasthenia gravis, and meningoencephalitis
- Events suggestive of hypersensitivity, infusion-related reactions, cytokine release syndrome, macrophage activating syndrome, and hemophagocytic lymphohistiocytosis
- Nephritis
- Ocular toxicities (e.g., uveitis, retinitis, optic neuritis)
- Myositis
- Myopathies, including rhabdomyolysis
- Grade ≥2 cardiac disorders (e.g., atrial fibrillation, myocarditis, pericarditis)
- Vasculitis
- Autoimmune hemolytic anemia
- Severe cutaneous reactions (e.g. Stevens-Johnson Syndrome, dermatitis bullous, toxic epidermal necrolysis)
- Myelitis
- Facial paresis

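### In neoadjuvant Arm C, Section 8.13 makes only atezolizumab wait for the steroid taper, and the Grade 3 or higher eye row stops atezolizumab but only pauses tiragolumab

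*Combined protocol and SAP*

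**What the plan says.** The point concerns neoadjuvant Arm C only, because adjuvant treatment is atezolizumab alone (Section 7.3).

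- **Section 8.0** tells sites to follow the modification tables strictly during neoadjuvant treatment.
- **Section 8.13** is triggered when either antibody is withheld and corticosteroids are started for an adverse event. The taper must run over at least 1 month to 10 mg/day or less of "oral prednisone or equivalent before atezolizumab can be resumed". A later sentence lets study treatment be withheld beyond 105 days "to allow for patients to taper off corticosteroids prior to resuming treatment".
- **Table 8.22, AST/ALT Grade 3**, has the same text for both drugs: "Omit and initiate systemic steroid treatment (see Section 9.0) Consult Hepatology if not improving within 1 week Resume when symptoms resolve to" Grade 1 or lower. The row has no taper condition.
- **Section 9.661, Grade 3 or 4**, gives 1-2 mg/kg/day prednisone and continues: "If event resolves to Grade 1 or better, taper corticosteroids over" at least 1 month. Section 9.684 sets the same dose and the same taper start for Grade 3 or 4 ocular events.
- **Table 8.22, eye disorders Grade 3 or higher**, reads "Omit until $\leq$ Grade 1" for tiragolumab and discontinue for atezolizumab.
- **The opening of 8.22** recommends delaying the second drug when the first is delayed, because the safety profiles are similar. Its next paragraph foresees one drug being given while the other is delayed.
- **Section 10.561** lists ocular toxicities and hepatitis as events of special interest for atezolizumab and/or tiragolumab.

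**The concern.** The trigger in 8.13 names two drugs and the condition binds one. Where a table row lets tiragolumab resume at the moment the taper begins, nothing in 8.13, table 8.22 or Section 9 makes it wait. A compliant site can then give tiragolumab on high-dose steroids while atezolizumab is barred until 10 mg/day or less. After a severe eye event the 8.13 condition never operates, because atezolizumab has been stopped for good. Tiragolumab could then continue as a single agent after an event judged serious enough to end its partner.

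Three things are at stake: patient safety after a severe immune-mediated event, uniform handling of the same event across sites, and the regimen being estimated. Section 16.1112 counts every patient who starts neoadjuvant treatment towards the pCR rate of the combination. Resuming tiragolumab alone also means that not all study drugs are omitted, so the 28-day route to surgery in 8.2 is not reached.

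**Working it through.** The plan gives no figure to reproduce. The check is a comparison of rules plus a dose count.

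**1. Liver sequence.** At AST/ALT Grade 3 both drugs are omitted and steroids start (8.22). At Grade 1 or lower, 8.22 permits both to resume and 9.661 starts the taper. Section 8.13 then holds atezolizumab for at least 1 month more. No parallel text holds tiragolumab.

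**2. Eye row against the rest of 8.22.** Counting by event and grade:

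| Rows of 8.22 | Count |
|---|---|
| All rows | 41 |
| Same action for both drugs | 39 |
| Action depends on the causal drug (CRS) | 1 |
| Different action (eye, Grade 3 or higher) | 1 |
| Discontinue atezolizumab whatever the causal drug | 16 |
| Of those 16, also discontinue tiragolumab | 15 |

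The 16 rows are: eye Grade 3 or higher; diarrhea/colitis 4; pancreatitis 4; infusion reaction 3 or higher; allergic reaction 3 or higher; HLH/MAS; the myasthenia, Guillain-Barré and meningoencephalitis group; AST/ALT above 10 x ULN; bilirubin above 2 x ULN; acute kidney injury 3 or higher; pneumonitis 3 or higher; maculo-papular rash 4; SJS; TEN; DRESS; other Grade 4.

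**3. Tiragolumab doses inside a taper.** Inputs: 4 cycles of 21 days (7.13) and a taper of 30 days, taking 1 month as 30 days. Let *o* (0 to 20) be the days from taper start to the next scheduled infusion. A second date falls inside the window if o + 21 < 30, that is o = 0 to 8. So 9 of 21 start days give two dates and 12 give one, provided doses remain. After dose *k* at most 4 − k remain:

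| Event after dose | Most doses in taper, min(2, 4 − k) | Most given alone after eye event, 4 − k |
|---|---|---|
| 1 | 2 | 3 |
| 2 | 2 | 2 |
| 3 | 1 | 1 |
| 4 | 0 | 0 |

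These are upper bounds. Omitted doses are not made up (8.2), so slow recovery can bring any of them to 0. The ranges are 0-2 and 0-3.

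**4. Steroid level at those doses (illustration).** Assume 60-100 kg and a linear taper. The starting dose S runs from 60 × 1 = 60 to 100 × 2 = 200 mg/day, and the dose on day d is S − (S − 10) × d/30.

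- First date, d = 0 to 20: lowest 60 − 50 × 20/30 = 26.7; highest 200 mg/day. This is about 2.7 to 20 times the 10 mg/day ceiling.
- Second date, d = 21 to 29: lowest 60 − 50 × 29/30 = 11.7; highest 200 − 190 × 21/30 = 67 mg/day. This is about 1.2 to 6.7 times the ceiling.

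**The case against.** **Read as a whole, the text already protects the patient.** The opening of 8.22 recommends joint delay, 8.2 lets providers hold doses beyond the table, 8.13 allows study treatment to be withheld for a taper, and Section 9.6 describes itself as guidance. This stands to the extent that a cautious site would hold both drugs after the liver event. But each of these texts is permissive, whereas 8.0 asks for strict adherence to the table. The joint-delay recommendation covers delay and not discontinuation, so it does not reach the eye row.

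**The eye cell may be deliberate.** Section 15.17 lists intraocular inflammation for atezolizumab. Section 15.47 names no eye toxicity for tiragolumab, and Appendix III mentions ocular toxicity only within a general potential risk. The CRS row shows that the table can separate the drugs, and the Investigator's Brochure is not available here. A deliberate distinction cannot be ruled out. However, the CRS row separates by causal drug and says so. The eye row gives no reason, and it sits against the similarity statement in 8.22 and the joint listing in 10.561.

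**Two tempting readings are not supported.** A reader might infer that Arm C lacks a partner-drug rule by mistake, because 8.13 says that if atezolizumab is discontinued in Arm B, "then cobimetinib should be discontinued, as single agent activity is not expected". That rationale is specific to cobimetinib; Section 15.41 suggests that tiragolumab may be active as a single agent. A reader might also infer that the eye cell was carried over from 8.21, where the vemurafenib cell begins the same way ("Omit until $\leq$ Grade 1 Resume with dose reduced by 1 level once $\leq$ Grade 1"). The resemblance is real, but the documents cannot show how the cell was drafted.

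**Conclusion.** The concern holds for two rows of 8.22. After AST/ALT Grade 3, tiragolumab may resume alone as the taper starts. After an eye event of Grade 3 or higher, it may resume although atezolizumab was discontinued. The eye cell does not use the word resume, but omitting a drug until a grade is reached implies it. The size is 0-2 doses within a 30-day taper and 0-3 doses alone after an eye event. The dose counts rest on the planned 21-day schedule; the mg/day figures also rest on the assumed body weight and linear taper.

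Three stronger statements go too far:

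- The protocol does not instruct sites to give tiragolumab on high-dose steroids. It fails to prevent it.
- Other rows might be thought to share the explicit overlap: colitis Grade 3, pancreatitis Grade 3, acute kidney injury Grade 2, pneumonitis Grade 2, maculo-papular rash Grade 3, hypophysitis and adrenal insufficiency. Section 9 prescribes 1-2 mg/kg/day steroids there but does not tie the taper start to Grade 1, so overlap is only an inference.
- No harm, and no shift in pCR or RFS, is demonstrated. The number of patients affected cannot be estimated from the documents.

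This is a cheap safety clarification that should be made, not a flaw that undermines the trial.

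**What to change.** 1. In Section 8.13, insert *or tiragolumab* after atezolizumab in the clause that sets the condition for resuming.
2. In table 8.22, eye disorders Grade 3 or higher, set the tiragolumab cell to *Discontinue*, as in the other 15 rows.

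The edit is one clause and one cell. The real cost is fewer neoadjuvant doses for some patients. With both drugs held for a taper of at least 30 days, the hold counted from event onset always exceeds the 28-day limit in 8.2. Counted from the first missed infusion it depends on *q*, the days from last dose to Grade 1, because dosing resumes on the first multiple of 21 at or after q + 30:

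- q up to 12: resume on day 42, so 42 − 21 = 21 days, within the limit.
- q from 13 to 33: resume on day 63, so 63 − 21 = 42 days, over the limit.

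Joint holds will therefore often send the patient to surgery once stable. Sections 8.2 and 13.12 already allow that, so no change to 8.2 is required. Whether to exempt taper holds is a clinical choice for the sponsor. The 105-day limit in 8.13 exceeds the 4 × 21 = 84-day course and can stay.
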